4.4.1. Rescue Medications

As soon as the patient has a drop in FEV1 of 20% and/or asthma symptoms, the patient will be removed from the EEU and will be treated with short-acting β 2 agonist every 20 minutes for 1 hour if necessary. Patients will stay under supervision in the observation room during 6 hours after leaving the EEU and FEV1 will be monitored every 30 minutes. During this 6-hour monitoring period, a LAR can appear with a drop in FEV1 of 15% and will be treated with short-acting β 2 agonist and corticosteroids if necessary.

After each allergen challenge, all patients will leave the site with a rescue treatment kit containing: short-acting β 2 agonist, oral corticosteroids, and oral antihistamines. The patients will also receive oral and written information about the procedure to be followed in case of the occurrence of AEs which may be related to the study, as well as the telephone number of the physicians of the study.

4.5. Efficacy Variables

4.5.1. Primary Efficacy Variables

The primary endpoint in the study is the time to EAR upon Controlled Cat Allergen Challenge in an EEU on day 8. The time to EAR will be defined as the time to a $\geq 20\%$ reduction in FEV1 or when the patient voluntarily departs the EEU due to clinically significant allergic and/or asthma symptoms. During the allergen challenges (post-randomization), the patient may remain in the EEU for a maximum of 4 hours. If a patient does not experience an EAR and remains in the EEU for the maximum time, their time to EAR will be censored at 4 hours. Censoring implies that the time to EAR is at least 4 hours, but the exact time is unknown.

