During the Cat Allergen Challenge, standardized cat allergen extract (40 ng/m^3) is continuously nebulized into the EEU and patients perform spirometry every 10 minutes until they experience bronchoconstriction, when their FEV1 is reduced by  $\geq 20\%$ , defined as an EAR. Patients leave the EEU once they achieve an EAR, and they are then monitored outside of the EEU in an observation room for 6 hours. Patients who fail to achieve an EAR within 2 hours in the baseline Cat Allergen Challenge in the EEU will be excluded from the study. During the time they are in the EEU, they record their TNSS, a validated, patient-reported, composite symptom assessment of congestion, itching, rhinorrhea, and sneezing, and TOSS, a validated, patient-reported, composite symptom assessment of ocular symptoms (itching, redness, tearing, and swelling) using handheld tablets every 20 minutes. During the 6-hour observation

---

---

period after leaving the EEU, FEV1 is measured every 30 minutes to assess for a late asthmatic response (LAR), defined as a delayed drop of 15% after exiting the EEU. During the 6-hour observation period, TNSS, TOSS, and chest symptom questions are recorded every hour. At the end of the 6-hour monitoring period, patients are discharged home if FEV1  $\geq$ 90% of the baseline value; if FEV1 is <90% of the baseline value, patients will continue to be monitored at the clinic until the patient meets criteria for discharge. FEV1 is monitored during 6 hours after the EEU session using portable spiroometers, and patients are followed up 18 hours after leaving the clinical unit. Patients meeting eligibility criteria are randomized to a single dose of REGN1908-1909 (600 mg SC) or placebo. Patients then return to the study site to undergo a 4-hour Cat Allergen Challenge in the EEU on days 8, 29, 57, and 85 with a 6-hour observation period, at which time EAR, TNSS, and TOSS are assessed using the same time points that were used at baseline. Exploratory measures are also assessed at baseline and throughout the study, as detailed in the exploratory objectives section.

---

Study Duration	The duration of the study for a patient is approximately 16 weeks, excluding the screening period.
End of Study Definition	The end of study for this study is defined as the last visit of the last patient.
Population	
Sample Size:	Approximately 60 patients with GINA 1 asthma sensitized to cat allergen.

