## **3. HYPOTHESIS AND RATIONALE**

### **3.1. Hypothesis**

A single SC dose of REGN1908-1909 600 mg (anti-Fel d 1) will reduce cat allergen-induced bronchoconstriction, as measured by an increase in time to EAR upon Cat Allergen Challenge in an EEU, in cat-allergic asthmatic patients not living with a cat compared to placebo-treated patients.

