#### **6.2.1. Inclusion Criteria**

A patient must meet the following criteria to be eligible for inclusion in the study:

1. Generally healthy men and women between the ages of 18 and 65 inclusive at the time of screening.
2. Documented or patient reported history (for at least 2 years) of symptomatic cat allergen-triggered asthma with rhinitis with or without conjunctivitis as defined by all of the following criteria:
  - a. Positive skin prick test (SPT) with cat hair extract (mean wheal diameter at least 5 mm greater than a negative control) at screening
  - b. Positive allergen-specific IgE (sIgE) tests for cat hair and Fel d 1 (>0.35 kAU/l at screening)
  - c. History of asthma GINA 1
  - d. Screening FEV1  $\geq$ 70% predicted after withholding long-acting  $\beta$ 2-agonists for > 36 hours and short-acting  $\beta$ 2-agonists for > 6 hours
  - e. Demonstrated  $\geq$ 20% fall in FEV1 within 2 hours during Cat Allergen Challenge in EEU and ability to withstand exposure for at least 10 minutes during screening
3. Willing and able to comply with clinic visits and study-related procedures
4. Provide informed consent signed by study patient or legally acceptable representative

5. Patients covered by health social identification number
6. Able to understand and complete study-related questionnaires
7. No cat exposure at home for the past year and must continue having no exposure at home during the study; cat exposure outside of the home shall be avoided for at least 1 week prior to any Cat Allergen Challenge and during the defined follow-up period.
8. Less than 10 pack-years of smoking history

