#### **10.4.3. Efficacy Analyses**

##### **10.4.3.1. Primary Efficacy Analysis**

The time to EAR will be defined as the time to a  $\geq 20\%$  reduction in FEV1 or when the patient voluntarily departs the EEU due to clinically significant allergic and/or asthma symptoms. The time to EAR for each treatment will be examined using Kaplan Meier estimates with patients being censored at 4 hours if they did not experience an EAR and remained in the EEU for 4 hours. If a patient leaves the EEU before experiencing an EAR and for reasons unrelated to their clinical symptoms, they will be censored at the time of EEU departure. The median time to EAR for each treatment group and the corresponding 95% confidence intervals will be presented for each Controlled Cat Allergen Challenge. A formal comparison of time to EAR in the treatment groups at day 8 will be performed using a Cox proportional hazards model, adjusting for allergen exposure and time to EAR in the baseline Cat Allergen Challenge. The ratio of Fel d 1 IgE to Cat Hair IgE at baseline will also be explored as potential covariate in the model. In patients who receive EEU related medications (including medications given on-site and rescue medications taken at-home), the impact of the carryover of medications between challenges will be explored. A one-sided statistical test of the hazard ratio for placebo compared to drug will be performed.

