1.2. Study Objectives

1.2.1. Primary Objectives

The primary objective of this study is to evaluate the prophylactic efficacy of REGN1908-1909 (anti-Fel d 1) administered as a single dose on day 1 in cat-allergic asthmatic patients (not living with a cat) in the prevention of a Controlled Cat Allergen Challenge-induced early asthmatic response (EAR) assessed by measures of lung function (FEV1) compared to placebo-treated patients on day 8.

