5.6. Analyses of Efficacy Variables

The primary endpoint is the time to EAR upon day 8 Controlled Cat Allergen Challenge in an EEU. The time to EAR will be defined as the time to a $\geq 20\%$ reduction in FEV1 (adjudicated by the blinded investigators) or when the patient voluntarily departs the EEU due to clinically significant allergic and/or asthma symptoms. During the post-randomization allergen challenges, the patient may remain in the EEU for a maximum of 4 hours. If a patient does not experience an EAR and remains in the EEU for the maximum time, their time to EAR will be censored at 4 hours. Censoring implies that the time to EAR is at least 4 hours, but the exact time is unknown. The statistical model will be a cause-specific Cox's proportional hazards model to compare the hazard ratio of EAR on day 8 in REGN1908-1909-treated patients to placebo-treated patients. This model allows for covariate adjustment for allergen concentration in the EEU on day 8 and the patient's time to EAR during the baseline Cat Allergen Challenge. Under this model, the hazard ratio is directly related to the ratio of median duration of tolerated exposure in the current challenge test on day 8, where a hazard ratio of 1 implies that the median duration of tolerated exposure in the 2 treatment groups is the same. The following null and alternative hypotheses of the primary endpoint will be tested:

H0: The hazard rate of EAR during the day 8 Controlled Cat Allergen Challenge is the same in patients receiving REGN1908-1909 and placebo (hazard ratio, HR = 1)

H1: The hazard rate of EAR during the day 8 Controlled Cat Allergen Challenge is lower (ie, the median duration of tolerated exposure is longer) in the REGN1908-1909-treated patients as compared to placebo-treated patients (HR < 1)

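### The primary early asthmatic response (EAR) event counts symptom-driven exits as well as FEV1 falls, and no EAR analysis or table separates the two

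*SAP*

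**What the plan says.** **The event.** SAP 4.5.1 and 5.6 and Protocol 10.4.3.1 define time to EAR as time to a fall in FEV1 of at least 20% or "when the patient voluntarily departs the EEU due to clinically significant allergic and/or asthma symptoms". The summary table in SAP 10.1 uses the same composite. The symptoms need not come from the lower airway.

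**The aim.** The primary objective (SAP 1.2.1) is prevention of an "early asthmatic response (EAR) assessed by measures of lung function (FEV1) compared to placebo-treated patients on day 8". Protocol 3.1 hypothesises that the drug "will reduce cat allergen-induced bronchoconstriction, as measured by an increase in time to EAR". The Study Design part of the Protocol synopsis describes the EAR by spirometry alone: patients are tested "until they experience bronchoconstriction, when their FEV1 is reduced by" at least 20%. Inclusion criterion 2e likewise requires a 20% "fall in FEV1 within 2 hours during Cat Allergen Challenge in EEU and ability to withstand exposure for at least 10 minutes".

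**The analyses.** SAP 5.6 says "The statistical model will be a cause-specific Cox's proportional hazards model". SAP 5.6.1 censors patients who complete 4 hours and those who leave for reasons unrelated to clinical symptoms. Kaplan-Meier, Cox, the rank-based fallback, Fisher's exact test, the per-protocol analysis and the analyses on days 29, 57 and 85 all use the composite.

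**Other FEV1 evidence.** Change and percent change in FEV1 AUC, including Day 8, is a secondary endpoint (SAP 4.5.2), called key in Protocol 10.2 and SAP 2.2. SAP 5.6.2 analyses it by MMRM with several sensitivity versions, and SAP 5.6.3 adds plots of percent change in FEV1. Nasal and ocular scores are analysed separately.

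**The concern.** The two components can respond differently. The drug is expected to reduce nasal and ocular symptoms, which are secondary objectives in their own right, and Protocol section 1 reports a 42% improvement in nasal symptom score at day 8 in an earlier nasal challenge study. Post-randomization challenges last up to 4 hours against 2 at screening, and Protocol 3.2.4 says rhinoconjunctivitis symptoms typically peak at 3 hours, so the longer exposure leaves more room for symptom exits.

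If such exits are a material share of events, a longer time to EAR could partly reflect better tolerance of rhinitis or conjunctivitis, while the report would read it as reduced bronchoconstriction. The primary analysis, its fallback and its sensitivity test would all share that ambiguity.

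**Working it through.** **1. The plan's own figure.** Inputs from SAP 2.2 and 4.5.1: medians 58 and 132 min, 30 per arm, 8 dropouts (so 26 per arm), one-sided 0.05, exposure up to 240 min. Assume exponential times.

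- Placebo hazard: ln 2 / 58 = 0.01195 per min.
- Expected events: placebo 26 × (1 − e^(−0.01195×240)) = 24.5; drug, HR 58/132 = 0.439, 18.6; total D = 43.15.
- Power = Φ(|ln HR| × √D / 2 − 1.645) = Φ(0.822 × 3.284 − 1.645) = Φ(1.056) = 85.5%.

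With HR 1/2.25 the result is 84.7%. The stated 84% reproduces.

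**2. Composite result with no effect on the FEV1 event.** Let s be the share of the placebo event hazard due to symptom exits, and h the drug's hazard ratio on those exits. Both are assumptions. Then composite HR = (1 − s) + s × h.

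Example, s = 0.30 and h = 0.2: HR = 0.70 + 0.06 = 0.76; D = 47.6; Φ(0.274 × 3.450 − 1.645) = Φ(−0.698) = 24%.

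| s | HR, h = 0.5 | P(positive) | HR, h = 0.2 | P(positive) |
|---|---|---|---|---|
| 5% | 0.975 | 6% | 0.96 | 7% |
| 10% | 0.95 | 7% | 0.92 | 9% |
| 20% | 0.90 | 10% | 0.84 | 15% |
| 30% | 0.85 | 14% | 0.76 | 24% |
| 40% | 0.80 | 19% | 0.68 | 37% |

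A log-rank simulation (3000 runs, FEV1 read every 10 min) at h = 0.2 gave 10%, 17%, 26% and 42% for s = 10% to 40%. In the same runs, an FEV1-only analysis that censored symptom exits was positive in about 5-6%. The simulation made the two event times independent, so its censoring was uninformative by construction.

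**3. Power of an FEV1-only analysis.** If the drug has the design HR on both components, FEV1 events are 43.15 × (1 − s):

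| s | FEV1 events | Power |
|---|---|---|
| 10% | 38.8 | 82% |
| 20% | 34.5 | 78% |
| 30% | 30.2 | 73% |
| 40% | 25.9 | 67% |

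**4. What the FEV1 AUC covers.** SAP 6.2 takes a time-averaged FEV1 over 0-2 hours and carries the last value forward after exit; 0-4 hours is a sensitivity version. The event window runs to 4 hours. SAP 5.6.2 attaches nominal p values. An average of FEV1 does not say how many primary events were FEV1 falls.

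**The case against.** A reader might infer that nothing in the plan isolates lung function, so that the trial could not tell nasal relief from bronchoprotection. The documents do not support that. FEV1 AUC on Day 8 is a pre-specified FEV1-only endpoint with a stated 88% power. If the benefit were only nasal and ocular, the symptom scores should improve while FEV1 AUC showed no advantage. Carrying values forward does not create a false FEV1 benefit here: a placebo patient who leaves for rhinitis carries a preserved FEV1. This stands, and it confines the point to the EAR analyses.

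A reader might also take the 7-37% as inflated type I error. It is not. The null hypothesis in SAP 5.6 is equal hazard of EAR as defined; in the scenario above that null is false.

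Symptom exits may also be few. Every patient must show a 20% FEV1 fall within 2 hours at screening, the assumed placebo median of 58 min is well before the 3-hour symptom peak, and SAP 1.2.3 notes that some patients were asymptomatic at baseline. Some symptom exits will be for asthma symptoms, which fit the objective better. All this is fair, but no rate is given, so it cannot settle the matter.

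Finally, the composite is deliberate and disclosed, and counting symptom exits as events avoids censoring patients who may be close to an FEV1 fall. That is a good reason to keep it as primary. Nor is the cause-specific label empty, since unrelated departures are censored; but it does not split the EAR into its components.

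**Conclusion.** The point holds in a limited form. A positive primary result would show longer tolerated exposure before an FEV1 fall or a symptom-driven exit; by itself it need not show less bronchoconstriction. No EAR analysis isolates the FEV1 fall and no table of components is planned. FEV1 AUC is relevant separate evidence but does not identify the component behind the primary result.

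The size depends on an unknown. At a 5% symptom share the composite would be positive in 6-7% of trials with no FEV1-event effect, close to the 5% reference. At shares of 10-40% the range is about 7-37%. These figures rest on assumed shares, assumed symptom-exit hazard ratios of 0.2-0.5, exponential times and 26 evaluable patients per arm. The primary test is valid for the event as defined, and the stated power is sound.

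**What to change.** Keep the composite as primary, with alpha and sample size unchanged. Add to SAP 5.6.1:

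- a supportive cause-specific Cox model for time to the adjudicated FEV1 fall of at least 20%, with symptom-only exits censored as a competing event and the primary model's covariates;
- cumulative incidence by component and arm (SAP 5.6.3 already allows a competing-risks method for the late response);
- a table of event type by arm at each challenge: FEV1 fall, symptom-only exit, unrelated departure, 4-hour completion.

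The table also needs a place for patients removed by staff. SAP 4.4.1 describes removal for asthma symptoms, while the event definition mentions only voluntary departure; the coding of the two should be reconciled.

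Specify this before the first-step analysis, which SAP section 7 makes the final analysis of the primary endpoint.

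The data cost is small: FEV1 is read every 10 minutes in the exposure unit, and the event definition already needs the reason for exit. The statistical cost is fewer events and lower power (section 3 of the working), and censoring of symptom leavers that may be informative. The supportive model should therefore be read with the composite and the FEV1 AUC, not in place of either.

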4.5.2. Secondary Efficacy Variable(s)

The secondary endpoints are:

- Time to EAR upon Controlled Cat Allergen Challenge in an EEU on days 29, 57, and 85

- Change and percent change in AUC of the FEV1 during a Controlled Cat Allergen Challenge over the exposure interval (maximum of 4 hours) from the baseline Controlled Cat Allergen Challenge to challenges on days 8, 29, 57, and 85
- Change in AUC of patient-assessed nasal symptoms induced by a Controlled Cat Allergen Challenge over the exposure interval (maximum of 4 hours) from the baseline Controlled Cat Allergen Challenge to challenges on days 8, 29, 57, and 85
- Change in AUC of patient-assessed ocular symptoms induced by a Controlled Cat Allergen Challenge over the exposure interval (maximum of 4 hours) from the baseline Controlled Cat Allergen Challenge to challenges on days 8, 29, 57, and 85
- Change and percent change in cat allergen quantity as experienced by patients during exposure (measured by Fel d 1 allergen concentration (ng/m³) x minute ventilation x time in hours) from the baseline Controlled Cat Allergen Challenge to challenges on days 8, 29, 57, and 85
- Incidence rates of treatment-emergent adverse events (TEAEs) and serious TEAEs through end of study

Total Nasal Symptom Score

Total nasal symptom score is from 0 to 12 and is based on assessment of 4 nasal symptoms graded on a Likert scale ranging from 0 (none) to 3 (severe) for congestion, itching, and rhinorrhea, and from 0 (none) to 3 (5 or more sneezes) for sneezing.

Total Ocular Symptom Score

Total ocular symptom score is from 0 to 12 and is based on a 4-point Likert scale ranging from 0 (none) to 3 (severe) for itching/burning, redness, swelling/puffiness, and tearing/watery eyes.

Spirometry

Study staff-supervised spirometry will be performed in all patients at visits shown in [Table 1](#) with a standard measurement of FEV1. FEV1 will be measured by means of spirometry at 10-minute intervals during placebo and cat allergen exposures in the EEU, every 30 minutes during the 6-hour observation period after leaving the EEU. Additional spirometry may be performed when prompted by asthma symptoms and/or at the discretion of the investigator. In the case where a patient has multiple spirometry efforts from the same time point, the study staff will select an effort for use in analysis based on the quality of the efforts as assessed by a flow volume loop.

At home spirometry will be performed hourly for approximately 18 hours after leaving the clinical unit, excluding hours when the patient is sleeping. Additional spirometry may be performed when prompted by asthma symptoms

Spirometry will be measured on the day of randomization prior to receiving the study drug and will be measured after 6 hours prior to leaving the clinic. At the end of the 6-hour monitoring period, patients will undergo a physical exam and vital signs, including spirometry, and will be discharged home if there are no abnormal findings and if FEV1 $\geq 90\%$ of baseline. Otherwise, in case of FEV1 is $< 90\%$ of the baseline value, patients will continue to be monitored at the clinic until the patient meets criteria for discharge.

Spirometry measurements include FVC (L), FEV1 (L), FEV1/FVC (%), PEF (L/s), FEF 25-75 (L/s). Minute ventilation (L/min) will also be measured using spirometry at screening 1 time while the patient is at rest, and this value will be used to calculate allergen exposure throughout the study (minute ventilation x Fel d 1 allergen concentration (ng/m³) x time (in hours)).

4.5.3. Exploratory Efficacy Variables

The exploratory efficacy variables are:

- Time to Late Asthmatic Response (LAR) on days 8, 29, 57, and 85
- Time to Any Asthmatic Response on days 8, 29, 57, and 85
- Change and percent change from FeNO (parts per billion) (adjusted for the pre-challenge baseline) from baseline to days 30 and 86
- Change and percent change in the skin prick test with serial allergen titration, measured by AUC of the wheal sizes (diameter) over log-transformed allergen concentrations with cat allergen from baseline to day 29, 85, and 113

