Exploratory objectives will assess total and allergen-specific IgE levels (cat hair, Fel d 1, Fel d 2, Fel d 4, Fel d 7) at baseline and on study drug; standard skin prick test with common allergens at baseline to assess poly-allergy; early-phase allergic skin responses as measured by skin prick test with serial allergen titration with cat hair extract at baseline, day 29, and day 85; nasal congestion in an EEU as measured by peak nasal inspiratory flow (PNIF) at the time of EAR and 6 hours after exposure; biochemical measures of asthma control as measured by fractional exhaled nitric oxide (FeNO) at baseline and 24 hours after EEU exposure; patient-reported chest symptoms in an EEU as measured by chest symptom questions every 20 minutes in the EEU and hourly for 6 hours after EAR; and changes in type 2 inflammation in the nasal mucosa as measured by RNA sequencing, measured at baseline and 6 hours after EEU exposure.

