## 2.3. Exploratory Objective(s)

### 2.3.1. Exploratory Efficacy Objectives

- To evaluate LAR on days 8, 29, 57, and 85
- To evaluate whether a single prophylactic SC administration of REGN1908-1909 inhibits a wheal-and-flare response to a skin prick test with serial allergen titration with cat allergen in patients with cat allergen-triggered asthma and AR with or without conjunctivitis on days 29 and 85
- To evaluate the prophylactic efficacy of REGN1908-1909 in cat-allergic patients not living with a cat to reduce respiratory symptoms induced by a Controlled Cat Allergen Challenge on days 8, 29, 57, and 85 as measured by chest symptom questions
- To assess the prophylactic effect of REGN1908-1909 on biochemical measures of asthma control (FeNO) in patients with cat allergen-triggered asthma induced by a Controlled Cat Allergen Challenge on days 30 and 86 and measured 24 hours after challenge
- To assess the prophylactic effect of REGN1908-1909 on TNSS, TOSS, and chest symptoms up to 24 hours after leaving the EEU
- To assess the prophylactic effect of REGN1908-1909 on objective measures of nasal congestion (PNIF) in patients with cat allergen-triggered asthma induced by a Cat Allergen Challenge on 8, 29, 57, and 85
- To assess the relationship between baseline cat allergen-specific IgE levels (cat hair sIgE, Fel d 1 sIgE), total IgE, and the ratio of cat allergen-specific IgE/total IgE (cat hair sIgE/total IgE and Fel d 1-specific IgE/total IgE levels) and efficacy of REGN1908-1909
- To assess the relationship between cat allergen-specific IgE levels (Fel d 2, Fel d 4, Fel d 7, and other common allergens) at screening and baseline to evaluate the relationship between response to REGN1908-1909 and poly/mono-sensitization
- To assess the extent of REGN1908-1909 interference with the measurement of endogenous anti-Fel d1 IgE in baseline samples and its relationship to clinical benefit
- To assess the degree to which REGN1908-1909 prevents induction of type 2 inflammation in the nasal mucosa as assessed by RNA sequencing of nasal brushing on day 29.

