### Assessments

Study staff-supervised spirometry will be performed in all patients at visits shown in [Table 1](#) with a standard measurement of FEV1 (Section [8.2.2.4](#)).

The asthma control test (ACT), which uses a 5-point Likert scale, will be used prior to the screening cat allergen EEU to determine whether the patient's asthma is well controlled, and again at the final safety follow-up study visit (Section 8.2.2.3).

Patient-reported allergic symptoms (nasal, ocular, and chest symptoms) will be recorded by patients using a 4-point Likert scale (Section 8.2.2.1, Section 8.2.2.2, and Section 8.2.2.3).

Measurement of FeNO, a marker of airway inflammation, will be analyzed from exhaled breath condensates obtained at baseline and 24 hours after the Controlled Cat Allergen Challenges during screening, on day 30 and day 86 (Section 8.2.2.5).

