8. Titrated SPT with Serial Allergen Titration with cat allergen will be performed at screening visit 3, days 29, 85, and 113. On days when an allergen challenge is performed, the test will be performed prior to allergen challenge.
9. FeNO is assessed during screening, Visit 4 and then 24 hours after EEU exposure at day 30 and day 86.
10. All safety assessments performed at screening have to be normal and checked against the inclusion/exclusion criteria prior to REGN1908-1909 administration on day 1 (baseline).
11. On day 1, vital signs are taken prior to PK draw, prior to REGN1908-1909 administration, and at 2 hours ( $\pm 10$  min) after completion of the injection.

12. Vital signs are taken prior to entry into the EEU, at exit from the EEU, and prior to leaving the clinical trial unit, and any additional times as needed.
13. Telephone call to collect AEs and concomitant medications, including any medications used from the rescue treatment kit, up to 24 hours after the EEU exposure.
14. Total blood draw at any visit will never exceed 60 mL. Blood volumes are never to exceed 350 mL in 12 weeks.
15. Samples are collected prior to administration of REGN1908-1909.
16. On day 1, urine pregnancy test is completed prior to administration of REGN1908-1909 in women of childbearing potential. Postmenopausal women do not need urine pregnancy testing.
17. Total IgE and allergen-specific serum IgE levels (Fel d 2, Fel d 4, Fel d 7).
18. Genomic analysis is mandatory for all patients enrolling in the study. One DNA sample is to be collected on day 1/randomization, but if this sample collection was omitted at baseline, it can be collected at any subsequent visit. [REDACTED]
19. PK samples are drawn at any time in the outpatient visit day from day 8 through day 113 (end of study) visit.
20. After exiting the EEU, patients are monitored outside the EEU in an observation room for approximately 6 hours.
21. Patients will be observed for 6 hours in the observation room after receiving a single dose of REGN1908-1909 or placebo.
22. Blood draws should be performed before the EEU exposure
23. Cat EEU visit 3 and visit 6 must be spaced at least 3 weeks apart
24. Assessments and procedures at the unscheduled visit(s) are to be performed at the discretion of the principle investigator.
25. Screening visits 1 and 2 may be combined into 1 visit if the patient has a historical, positive cat SPT or cat IgE that was completed in the last 12 months.

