### **8.2.3.4. Telephone Call**

Patients will be called approximately 24 hours after EEU exposure after the EEU visits on days 8 and 57. Phone calls will collect information on AEs and concomitant medications, including any asthma symptoms and medications used from the rescue treatment kit that the patient was sent home with after the EEU visit. During the call, study staff will recommend any further treatment and visit follow-up if needed based on investigator discretion.

NOTE: patients will return to the Alyatec site approximately 24 hours after the EEU exposure on days 29 and 85 for FeNO measurements, therefore they will not receive a telephone call after these visits per SOE ([Table 1](#)).

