hour observation period, or in the at-home monitoring period, will be treated as the event time. If the subject experiences no asthmatic reaction at a given Allergen Challenge visit, the patient's time will be censored at 24 hours. Kaplan-Meier estimates and curves will be produced for each visit.

The presence or absence of any asthma exacerbation (EAR or LAR) in the REGN1908-1909 treatment group as compared to placebo will be tested using a Fisher's Exact Test.

Individual spaghetti plots and mean plots of the percent change in FEV1 over time will also be examined. LOCF will be used in the calculation for any graphical displays of the mean change in FEV1 over the Cat Allergen Challenge.

The peak TNSS and TOSS and change from pre-challenge baseline to peak TNSS and TOSS across EEU challenge visits may also be examined using MMRM models.

The change and percent change from the Baseline Cat Allergen Challenge in the Fractional exhaled Nitric Oxide (FeNO) (adjusted for the pre-challenge baseline) will be explored using an MMRM model, with the treatment, visit, and treatment by visit interaction, and use of steroid rescue medications within 24 hours of the EEU challenge as factors. The time in EEU will be included as a covariate in the model.

The skin prick test with serial allergen titration with cat allergen will also be compared between treatment groups using an MMRM model, with the treatment, visit and treatment by visit interaction as factors.

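### The exploratory FeNO endpoint is adjusted for a pre-challenge value that is not collected for either post-dose challenge, and the SAP defines neither the value nor the adjustment

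*SAP*

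**What the plan says.** The SAP names the variable in 4.5.3: "Change and percent change from FeNO (parts per billion) (adjusted for the pre-challenge baseline) from baseline to days 30 and 86". The analysis text in SAP 5.6.3 makes the baseline challenge the comparator: "The change and percent change from the Baseline Cat Allergen Challenge in the Fractional exhaled Nitric Oxide (FeNO) (adjusted for the pre-challenge baseline". The MMRM described there has treatment, visit, their interaction and steroid rescue within 24 hours of the challenge as factors, and time in the EEU as the covariate.

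On timing, footnote 9 of the schedule (Protocol 8.1.1, repeated in SAP 10.2.1) says: "FeNO is assessed during screening, Visit 4 and then 24 hours after EEU exposure at day 30 and day 86". The FeNO row of Table 1 has four marks in both documents: V2, V4, V8 (Day 30) and V11 (Day 86). Protocol 8.2.3.4 agrees: "patients will return to the Alyatec site approximately 24 hours after the EEU exposure on days 29 and 85 for FeNO measurements". The Assessments text in Protocol 5.1 lists FeNO as "obtained at baseline and 24 hours after the Controlled Cat Allergen Challenges during screening, on day 30 and day 86", so it treats a baseline reading as distinct from the 24-hour readings.

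The objective in Protocol 2.3.1 speaks of FeNO "induced by a Controlled Cat Allergen Challenge on days 30 and 86 and measured 24 hours after challenge". Protocol 4.3 defines the variable more simply, as the FeNO level 24 hours after challenge, with no adjustment.

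**The concern.** The SAP wording promises a response to challenge: FeNO after exposure, corrected for FeNO before it, compared with the same quantity at the baseline challenge. The schedule cannot supply this for Day 29 or Day 85. A lower Day 30 value in the active arm could mean a smaller reaction to the previous day's exposure. It could also mean a lower resting level, for example because less inflammation remained from the Day 8 challenge, because corticosteroids had been given for an earlier late response, or because the drug changed background FeNO. The model term for steroid rescue covers only the 24 hours around the challenge.

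Pre-specification is also at stake. One phrase allows several different endpoints, and the SAP does not choose among them.

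**Working it through.** The plan states no figure for this endpoint, so there is none to reproduce. The check is a mapping of the schedule followed by algebra.

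**1. Schedule.** Reading the FeNO row of Table 1 against the visit header:

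| Cat challenge | FeNO before it | FeNO after it |
|---|---|---|
| Baseline (V3) | V2, an earlier screening visit | V4 |
| Day 29 (V7) | none in the same period | V8 (Day 30) |
| Day 85 (V10) | none in the same period | V11 (Day 86) |

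By contrast, footnotes 5 to 7 put spirometry, the symptom scores and PNIF before each cat challenge. FeNO is the exception.

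**2. Which reading is the baseline?** V2 is the only FeNO reading before any cat challenge. The general rule in SAP 6.1 takes the last valid value before dosing, which for FeNO is V4, itself a post-challenge value. The two rules point to different readings.

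**3. What the adjustment does if V2 is used.** Write D30 for the Day 30 value; Day 86 works the same way. The ppb values are illustrative, since the documents give no FeNO data: V4 = 60 and D30 = 50. The unadjusted change is 50 − 60 = −10 ppb, or −10/60 = −16.7%.

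- *Subtraction, absolute change:* (D30 − V2) − (V4 − V2) = D30 − V4 = −10 for any V2. The adjustment has no effect.
- *Subtraction, percent change:* (D30 − V4)/(V4 − V2).

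| V2 (ppb) | V4 − V2 | Percent change |
|---|---|---|
| 20 | 40 | −10/40 = −25% |
| 40 | 20 | −10/20 = −50% |
| 50 | 10 | −10/10 = −100% |
| 55 | 5 | −10/5 = −200% |
| 60 | 0 | undefined |
| 65 | −5 | −10/(−5) = +200% |

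The same 10 ppb fall gives almost any figure, and the sign reverses when V2 exceeds V4.

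- *Ratio to V2, percent change:* (D30/V2)/(V4/V2) − 1 = D30/V4 − 1 = −16.7% for any V2. It cancels again.
- *Change in percent-from-V2:* 100 × (D30 − V4)/V2 = −50.0, −25.0, −20.0 and −18.2 points for V2 = 20, 40, 50 and 55. It does not cancel.
- *V2 as a model covariate:* no cancellation, but the covariate is not among the listed terms.

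**4. Model.** SAP 5.6.2 lists a baseline-challenge covariate for FEV1 AUC and for allergen quantity. The FeNO model in 5.6.3 lists no FeNO covariate, neither V2 nor V4.

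**The case against.** The strongest reply has four parts.

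- **V2 is a pre-challenge baseline.** This stands. A reader might infer from the schedule that no FeNO precedes the baseline cat challenge, but V2 does; only a same-day V3 reading is missing. At baseline a pre-to-post change is obtainable as V4 − V2, on different days. Whether V2 FeNO is taken before or after the saline exposure is not stated.
- **Adjustment may mean a covariate.** This is fair, because SAP 5.6.1 and 5.6.3 use similar wording for Cox covariates. A reader might conclude that the adjustment always cancels. It does so for the absolute change under subtraction and the percent change under a ratio, and not in the other forms. But if a covariate is meant, the model description omits it.
- **Randomisation protects the comparison.** This also stands. Both arms follow one schedule under blinded 1:1 allocation, so season and drift since screening should balance and add noise rather than bias. A drug effect on resting FeNO would itself be a drug effect. It would be wrong to infer that the treatment comparison is invalid. What randomisation cannot do is attribute a difference in level to that day's challenge, because the competing explanations arise after dosing and may differ by arm.
- **The protocol asks only for a level.** Protocol 4.3 does, and the schedule delivers it. The objective in 2.3.1 does not expressly require a within-visit difference either. This supports bringing the SAP back to the protocol; it does not support the SAP's adjustment wording.

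**Conclusion.** The point holds in a limited form. Neither post-dose challenge has a preceding FeNO reading from its own period, so a challenge-induced FeNO change at Day 29 or Day 85 is not identifiable from the planned data. The adjustment named in the SAP is undefined. In its simplest form it either does nothing (absolute change) or produces an erratic percent change.

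This rests on Table 1 and footnote 9 being the full FeNO schedule, and on V2 being the intended reference, which the SAP does not state. The study manual, to which the protocol refers for procedural detail, was not available.

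The consequence is confined to one exploratory variable with no multiplicity control. It limits the mechanistic claim and leaves pre-specification incomplete. It does not bias the randomised comparison of post-challenge FeNO level, and it does not touch any primary or secondary analysis.

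**What to change.** In SAP 4.5.3 and 5.6.3, delete the parenthesis about pre-challenge adjustment. Analyse Day 30 and Day 86 FeNO by the planned MMRM with V4 and V2 FeNO added as covariates, and name both readings. Report the result as post-challenge FeNO level, in line with Protocol 4.3, and state that Days 29 and 85 have no pre-challenge reading. With V4 in the model at a common slope, modelling the level or the absolute change gives the same treatment estimate, so nothing is lost by dropping the change from V4.

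This needs only SAP wording and uses data already scheduled. Baseline covariates should also improve precision. The costs are a narrower mechanistic claim and the loss from the model of any patient without a V2 or V4 value; SAP 6.3 already excludes patients with a missing baseline from change analyses.

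FeNO readings before EEU entry at V3, V7 and V10 would allow the challenge-induced claim. They are added procedures that need an approved amendment under Protocol section 14. They also come late: SAP 1.2.3 records that baseline data had already been reviewed blinded, so V3 readings cannot be recovered for those patients. The wording change is the practical course.
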